Descriptive statistics for metric variables will be number of values analyzed (n), number of missing values (nmiss, if any), number of imputed values (nimip, where applicable), mean, standard deviation (SD), median, quartiles, minimum, and maximum. Mean, quartiles, and median will be reported to one decimal place more than the data were collected, for the SD two decimal places more will be displayed; for calculation of derived variables, the number of decimal places is given in the sections below and the number of decimal places to be displayed for descriptive statistics of metric derived variables is defined in [Appendix 8.7](#). For both collected and derived data, descriptive statistics for changes from study / Cycle 2 baseline, as applicable, will be displayed with the same number of decimal places.

⁶ including important and non-important PDs

Frequency tables for qualitative variables will be absolute and percent frequencies (n, %). Frequency tables will include the number of missing values, where applicable. If not specified otherwise, calculation of percentages will be based on all subjects from a specified population and treatment group with non-missing data at the respective visit. The denominator will be specified in a footnote to the tables for clarification if not otherwise obvious. Percentages will be reported to one decimal place.

If not otherwise specified, statistical tests will be conducted 2-sided at type I error rate 5%. P-values will be reported to four decimal places (e.g., $p=0.0375$). P-values below 0.0001 will be presented as '<0.0001'. Confidence intervals (CIs) will be 2-sided for 95% confidence level.

The last valid value before first administration of the investigational product (IP) will be analyzed as study baseline and the last valid value before IP administration in Cycle 2 will be analyzed as Cycle 2 baseline, but only considering data from Cycle 2 baseline visit (V8) and from control visit at Week 18 of Cycle 1 (V7).

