Derivation of maximum tremor amplitude at wrist level at study baseline (as defined at beginning of Section 4) according to Steps 1 to 3 (see above) is only meaningful if the three angular tremor amplitude values for flexion/extension, radial deviation/ulnar deviation and for pronation/supination levels are each available for all four tasks from all three assessments rounds. Likewise, maximum tremor amplitude at wrist level at Week 6 (V4) can only be calculated as described above if the three above-mentioned angular tremor amplitude values are each available for the selected task from all three assessment rounds. If any of these study baseline or Week 6 (V4) data are missing, the primary endpoint cannot be derived and will be considered as missing. Under the assumption of missingness at random (MAR), missing values will not be replaced for the primary analysis.

The confirmatory analysis of the primary efficacy endpoint will be based on the FAS-UP (OC) using least square means (LS Means) from a baseline-adjusted analysis of covariance (ANCOVA) as implemented in SAS PROC MIXED. Fixed class effects will be the treatment group (NT 201 versus placebo) and study site. Study baseline angular tremor amplitude at wrist level for the task with the maximum amplitude will be the fixed continuous covariate. Variances will be allowed to differ between treatment groups. Denominator degrees of freedom will be calculated according to the Kenward-Rodger method.

The difference in LS Means between treatment groups with associated 95% CI from this model will serve as an estimate for the size of the treatment effect. The two-sided t-test of the LS Mean treatment difference will be applied to the following testing problem at $\alpha_{2\text{-sided}}=5\%$:

$$H_0: \mu_{NT201} - \mu_{Placebo} = 0 \quad \text{vs.} \quad H_1: \mu_{NT201} - \mu_{Placebo} \neq 0,$$

where $\mu_{NT201} - \mu_{Placebo}$ denotes the expected mean treatment difference on the primary efficacy endpoint, with a negative difference indicating a treatment effect in favor of NT 201.

In case of convergence issues, study sites might be pooled for statistical analysis. Prior to unblinding, no need of pooling was seen for the primary analysis (see also Section 4.7.3).

SAS code similar to the following statements will be used:

```
PROC MIXED data = dataset;
  CLASS TRT01P (REF='C1 Placebo') SITEID;
  MODEL CHG = TRT01P SITEID BASE / solution ddfm=kr;

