4.1.2 Secondary Endpoints

4.1.2.1 Key Secondary Efficacy Endpoints

The two key secondary efficacy endpoints are defined in Section 2.2.1.2.1 and will be derived as follows:

- The value of the respective TETRAS score (TETRAS Performance dominant UL score and TETRAS ADL UL score) will be calculated for study baseline¹⁴ and for Week 6 (V4) as sum of all corresponding items as defined in Appendix 8.1 (see scores no. 5 and no. 2, respectively).
- Change from study baseline¹⁴ to Week 6 (V4) will be calculated by subtracting the value of the respective TETRAS score at study baseline from the respective value at Week 6 (V4), derived as described above.
- In case an item belonging to the respective TETRAS score is missing, the respective TETRAS score value cannot be meaningfully derived for the affected visit. Hence, derivation of each of the two key secondary endpoints requires that answers to all items belonging to the respective TETRAS score are available at both study baseline and Week 6 (V4). Otherwise, the respective key secondary endpoint will not be calculated and considered as missing.

The two key secondary efficacy endpoints will be tested with ANCOVA models similar to that for the primary analysis of the primary endpoint (see Section 4.1.1.1). However, the study baseline of the analyzed TETRAS score [i.e., TETRAS Performance dominant UL score (Score no. 5 in

¹⁴ For definition of study baseline see beginning of Section 4.

[Appendix 8.1](#)) or TETRAS ADL UL score (Score no. 2 in [Appendix 8.1](#)), as applicable] will be used for baseline adjustment. Handling of multiplicity is addressed in Section [4.7.2](#).

Missing data handling, pooling of study sites, exploratory sensitivity analyses (Section [4.1.1.2](#)), and supplementary analyses (Section [4.1.1.3](#)) will also be handled analogously to the respective analyses of the primary endpoint. For ANCOVA-based sensitivity analyses, the respectively analyzed TETRAS subscale score (see above) will be used. The multiple imputation based sensitivity analysis was planned to be performed in case of more than 10% missingness on the respective key secondary endpoint among all treated subjects. During the DRM performed on 17Jan2024 under double blind conditions, the two key secondary efficacy endpoints were found to be completely available for all treated subjects. It was hence concluded that multiple imputation is not required for key secondary endpoints.

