- Endpoints based on assessments of angular tremor amplitude in the bilateral treatment period will be derived analogously as described above for respective endpoints for the unilateral treatment period, but separately by motor dominant/ non-dominant UL as well as for the difference between both ULs. For all post-baseline visits in Cycle 2, changes will be derived as both changes from study baseline¹⁵ and as changes from Cycle 2 baseline for

¹⁵ For definition of study baseline see beginning of Section 4.

the motor dominant UL, as applicable. Changes from study baseline are only derived for motor-dominant UL because, in accordance with the visit schedules for treatment Cycles 1 and 2 in the CSP (see Tables 5 and 6), angular tremor amplitude of motor-dominant UL was only assessed in Cycle 2, i.e., no study baseline is available for the non-dominant UL.

- As defined in Section 4.1.1.1 for the primary efficacy endpoint, derivation of endpoints based on assessments of tremor amplitude generally requires that all respective assessments are available. Otherwise, the affected endpoint will be considered as missing.
- TETRAS based endpoints:
 - Endpoints based on TETRAS Performance by investigator and TETRAS ADL will be derived analogously as described in Section 4.1.2.1 for the two key secondary efficacy endpoints (see also Appendix 8.1 for assignment of TETRAS items to the different TETRAS scores).
 - Endpoints based on TETRAS Performance assessments by IRP: Values will be derived as medians over all available scores from IRP members: First, the respective TETRAS score (Score no. 5 in Appendix 8.1) will be calculated for each IRP member. Second, the median over the respective TETRAS score from all IRP members will be computed and rounded by 3 decimals whereby median will only be calculated if score is available for at least 2 out of 3 IRP members. Changes from study baseline will be calculated based on these medians.
 - As TETRAS based endpoints will only be calculated if answers to all respective items are available.
- Endpoints based on QUEST dimension and total scores:

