The results of a previous study [4] suggest that a treatment effect of about one standard deviation might be expected. For a 5% type I error and a randomization ratio of 2:1 a total sample size of 51 analyzable subjects is required to achieve 90% power. In order to account for uncertainty in parameter estimates and drop-outs it has been decided to randomize approximately 75 subjects.

6 Changes in the Planned Analyses

Compared to CSP version 3.0 dated 31-May-2021 and amendment 1 to CSP version 3.0 dated 26-MAY-2023, the following change to planned analyses is included in this SAP:

Sections [2.2.1.2.2](#) and [2.2.1.3](#):

- For precision, “as assessed by the investigator” was added to the definition of all other secondary endpoints and all other efficacy endpoints that are based on the TETRAS performance assessments in the bilateral treatment period. In accordance with the CSP, the IRP did not perform any assessments in Cycle 2.

Section [2.2.1.3](#):

- In the definition of other efficacy endpoints for the bilateral treatment period (Cycle 2) based on angular tremor amplitude assessments, the word “difference” was missing in the CSP and therefore added in part c) of the definition before “between both ULs”.
- The following restriction was added to definition of other efficacy endpoints for the bilateral treatment period (Cycle 2) based on angular tremor amplitude assessments:
“Changes from study baseline are only analyzed for motor-dominant UL because, in accordance with the visit schedules for treatment Cycles 1 and 2 in the CSP (see Tables 5 and 6), angular tremor amplitude of motor-dominant UL was only assessed in Cycle 2.”

Section 3:

- In the definition of the FAS-UP, “study baseline (V2)” was changed to “study baseline” and in the definition of the FAS-BP, “Cycle 2 baseline visit (V8)” was changed to “Cycle 2 baseline”.

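### The primary endpoint is set to missing when a single repeat round of a required TremorTek task is lost, although a task mean can be formed from two of the three rounds

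*SAP*

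**What the plan says.** Each 20-second recording yields three wrist-axis amplitudes, which are combined into one RMS value. Step 2 averages that RMS over three rounds of the same task. Step 3 picks the task with the largest mean at baseline. The Week 6 value is the three-round mean for that same task (SAP 4.1.1.1; Protocol 12.3.1.1).

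SAP 4.1.1.1 then adds a completeness condition. At baseline the three axis values must exist "for all four tasks from all three assessments rounds". At Week 6 they must exist for all three rounds of the selected task. Otherwise, "If any of these study baseline or Week 6 (V4) data are missing, the primary endpoint cannot be derived". Missing values are not replaced in the primary analysis, which assumes missing at random.

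Four other provisions bear on this:

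- **Baseline.** The opening of SAP Section 4 defines study baseline as the last valid value before the first injection. SAP Section 6 confirms that a V1 score can bring a subject into the FAS-UP when V2 has none.
- **Imputation.** Multiple imputation is run if more than 10% of the primary endpoint is missing in either arm, on all treated subjects. It is a sensitivity analysis read descriptively (SAP 4.1.1.2).
- **Rater panel.** For the panel score, the "median will only be calculated if score is available for at least 2 out of 3 IRP members" (SAP 4.1.3).
- **Blinded data review.** According to SAP 4.1.2.1, "the two key secondary efficacy endpoints were found to be completely available for all treated subjects". No such statement is made for the primary endpoint.

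**The concern.** The condition treats two kinds of completeness alike. Completeness across tasks is necessary, because the maximum of four task means cannot be identified when one is absent. Completeness across rounds is not. The rounds are repeats of one task, and a mean of two estimates the same quantity as a mean of three, with somewhat more noise, provided the rounds are exchangeable.

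FAS-UP membership needs only one baseline and one post-baseline amplitude score. A subject can therefore be in the FAS-UP and still leave the confirmatory model because one Week 6 round is missing. No planned analysis recovers the remaining rounds. The imputation model works on derived visit values, so partial recordings do not enter it. Under SAP footnote 10, an underivable baseline means that the Week 6 value is imputed too, even when the Week 6 recordings are complete.

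The protocol has no rule for a missing round, and SAP Section 6 does not list the completeness condition as a change. At stake are precision in the confirmatory analysis and how far it depends on missing at random.

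**Working it through.** **1. Reproduce the planned sample size.** SAP Section 5 says that prior results "suggest that a treatment effect of about one standard deviation might be expected" and that with "a randomization ratio of 2:1 a total sample size of 51 analyzable subjects is required to achieve 90% power". For a two-sample t-test (noncentral t, two-sided 5%, difference 1 SD), 34 + 17 = 51 gives power 0.910 and 32 + 16 = 48 gives 0.892. So 51 is reproduced as the smallest 2:1 total reaching 90%. With 50 + 25 = 75 the power is 0.981. The margin is (75 − 51)/75 = 32%.

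**2. Count the recordings that matter.** Baseline: 4 tasks × 3 rounds = 12. Week 6: 1 task × 3 rounds = 3. The endpoint depends on 15 recordings (45 axis values). The other nine Week 6 recordings are irrelevant to it.

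**3. Loss under the SAP rule.** Let p be the probability that a recording fails. The documents do not give p. I assume 1%, 2% and 3%, independent across recordings.

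- No V1 fall-back: loss = 1 − (1 − p)^15.
- A complete V1 set may replace an incomplete V2 set: with b = 1 − (1 − p)^12, loss = 1 − (1 − b²)(1 − p)³.

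At p = 1%, b = 0.1136 and (1 − p)³ = 0.9703. The loss with fall-back is 1 − (1 − 0.0129)(0.9703) = 4.2%.

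| p | Loss, V1 fall-back | N left of 75 | Power at 1 SD | CI widening | Loss, no fall-back | N left | Power at 1 SD |
|---|---|---|---|---|---|---|---|
| 1% | 4.2% | 71.8 | 0.976 | 2.2% | 14.0% | 64.5 | 0.961 |
| 2% | 10.2% | 67.3 | 0.968 | 5.6% | 26.1% | 55.4 | 0.931 |
| 3% | 17.3% | 62.0 | 0.955 | 10.0% | 36.7% | 47.5 | 0.889 |

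CI widening is 1/√(1 − loss) − 1. Pooled missingness reaches 10%, the level of the imputation trigger, at p of about 2.0% with fall-back and 0.7% without (1 − 0.9^(1/15)). Without fall-back the margin down to 51 is used up at p of about 2.5% (1 − (51/75)^(1/15)).

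**4. Loss under a two-of-three rule.** A task mean fails when at least two of three rounds fail: t = 3p²(1 − p) + p³, which is 0.00030, 0.00118 and 0.00265. With V1 fall-back, loss = 1 − [1 − (1 − (1 − t)^4)²](1 − t) = 0.03%, 0.12% and 0.28%. Without fall-back, 1 − (1 − t)^5 = 0.15%, 0.59% and 1.3%.

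**5. The opposite extreme: only whole sessions fail.** If all recordings of a session fail together with probability p, the loss with fall-back is 1 − (1 − p²)(1 − p) = 1.0%, 2.0% and 3.1%. Without it, 1 − (1 − p)² = 2.0%, 4.0% and 5.9%. A two-of-three rule recovers none of these.

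**6. A smaller effect.** At an assumed 0.8 SD, power is 0.897 with all 75 subjects. At p = 1% without fall-back it is 0.847.

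**The case against.** **Size is not established.** Every loss above rests on an assumed p and on independence. Sensor, calibration or transfer faults could take out a whole session, and step 5 shows that the problem then shrinks and the proposed rule gains nothing. Device instructions are in a separate manual (Protocol 9.1.1.2.1), so failed recordings may be repeated on the spot. Protocol 11.3 plans completeness checks on TremorTek data. This stands.

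**The rule has a rationale.** Protocol Step 2 specifies a mean of three rounds, and the SAP applies it literally. It also requires all items for TETRAS scores and all applicable items for QUEST. The rater-panel rule is an imperfect parallel: it is a median over raters for a descriptive endpoint. A two-round mean is noisier, and a maximum over task means slightly favours noisier ones. These are reasons for keeping a sensitivity analysis; they do not justify discarding two good rounds.

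**Stronger readings that a reader might infer, and that the documents do not support:**

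- *Any failed recording loses the subject.* Only three of the 12 Week 6 recordings count, and V1 may stand in for V2. The SAP does not say whether valid means a complete set, and footnote 10 still foresees an underivable baseline.
- *Complete TETRAS data prove that every missing primary value is a partial recording.* They suggest that the visits took place. They do not exclude sessions never recorded, lost, or done on the wrong arm, which SAP 4.1 foresees and only lists.
- *Silence about the primary endpoint at the blinded review means that much was missing.* No figure is given either way.
- *Failures are selective.* This is possible but not shown. Inclusion criterion 7 requires ability to perform all four tasks at screening and baseline.
- *Imputation replaces real data in the main result.* It is descriptive only and leaves the confirmatory estimate unchanged.

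**Conclusion.** The concern holds in a limited form. The all-rounds condition can remove subjects with usable repeat measurements from the confirmatory analysis; the documents give no reason for requiring every round, and no planned analysis uses the rounds that remain.

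How many subjects are affected cannot be determined. Under independent failures at 1% to 3% per recording, about 3 to 13 of 75 would be lost with V1 fall-back; session-level failure at the same rates would lose about 1 to 2. At 1 SD, power with fall-back stays at or above 0.955 across the range, so the trial is not put at risk. The expected cost is a confidence interval about 2% to 10% wider under independence, and more weight on missing at random. Power is less protected if V1 cannot stand in for V2 or if the effect is smaller than planned. This is a cheap improvement to precision, not an error that invalidates the primary analysis.

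**What to change.** If the data are still blinded, replace the condition in SAP 4.1.1.1 with the following, and record it in SAP Section 6:

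- A task mean is derived when at least two of its three rounds have all three axis values.
- Baseline is derivable if all four task means are derivable at V2; otherwise the V1 set is used, under the same condition.
- Week 6 is derivable if at least two of three rounds of the selected task are complete.
- The all-rounds-complete derivation is kept as a sensitivity analysis.

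This also settles what counts as a valid baseline. SAP 4.1.3 applies the same completeness principle to the other TremorTek endpoints and should be aligned.

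The cost is a few sentences and a few lines of derivation code. For the subjects affected, two-round means are slightly noisier and may slightly influence which task is selected. The rule does not rescue wholly lost or wrong-arm sessions. SAP version 1.0 (24 January 2024) postdates the blinded review of 17 January 2024, so the amendment should state that it was made blind.

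If unblinding has occurred, keep the prespecified primary analysis, add the two-of-three version as a labelled supplementary analysis, and report by arm how many subjects were lost to incomplete recordings.

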4.1.1.2 Sensitivity Analyses

If not specified otherwise, the exploratory sensitivity analyses described in the following will be performed on the FAS-UP (OC). Study sites might be pooled for statistical analysis to overcome convergence issues in ANCOVA models. Prior to unblinding, the need of pooling was only seen for sensitivity no. 2 (see below and Section 4.7.3).

- *Sensitivity analysis no. 1:* The ANCOVA model specified in Section 4.1.1.1 will be repeated on the PPS (OC).
- *Sensitivity analysis no. 2:* For the analysis of the treatment-by-pooled site interaction, study sites from the United States of America [USA] and Canada will be grouped together (“North American [NoA] sites”) and compared vs. all remaining study sites from Poland (“Polish [Pol] sites”). The ANCOVA model specified in Section 4.1.1.1 will be modified as follows to estimate treatment effects by pooled study site: The fixed effect study site will be replaced by fixed effects for pooled study site [NoA vs. Pol] and the treatment-by-pooled study site interaction. Apart from the respective modifications in the MODEL and LSMEANS statement, the SAS code will be identical to the one provided in Section 4.1.1.1. LS-Means by treatment group and LS Mean treatment differences will not only be provided overall but also by pooled study site (NoA vs. Pol).⁸
- *Sensitivity analysis no. 3:* Gender⁹ (as fixed class effect) and age (as fixed continuous covariate) will be added to the model specified in Section 4.1.1.1. The SAS code will be similar to the one provided there, with the only modification that gender⁹ and age will be added to the MODEL statement and gender⁹ additionally to the CLASS statement. The same statistics as those specified in Section 4.1.1.1 (with p-values for all fixed class effects and the fixed continuous covariates in the model) will be displayed.
- *Sensitivity analysis no. 4:* In case more than 10% missingness on the primary efficacy endpoint occurs in either treatment group among all treated subjects, multiple imputation of missing maximum tremor amplitude measurements at wrist level at study baseline and at Week 6 (V4)^{10,11} will be performed and results for the primary efficacy endpoint from an ANCOVA

⁸ In the CSP, a model “with treatment-by-site interaction to estimate treatment effects by site” was planned, with the option to pool sites for statistical analysis and the statement that “the necessity and details of pooling will be determined under double blind conditions”. To avoid convergence issues due to the high number of study sites in relation to the number of subjects to be analyzed, it was decided prior to unblinding to pool sites (NoA sites vs. Pol sites) for this interaction analysis. This adaption is thus not considered as a change from analyses planned in the CSP.

⁹ Standard name for variable is ‘sex’ in CDISC SDTM/ADaM.

¹⁰ Note that in case the task with maximum amplitude at wrist level at study baseline cannot be derived due to missing or incomplete assessments of tremor amplitude at wrist level at study baseline, the respective value at Week 6 (V4) cannot be derived either and hence needs to be imputed as well, even if TremorTek measurements of angular tremor amplitude at wrist level are completely available at Week 6 (V4) or not.

¹¹ Maximum tremor amplitude at V3/V4 to be calculated for the task with maximum tremor amplitude at study baseline.

model (as described in Section 4.1.1.1) applied to 1000 completed datasets will be combined for statistical inference. This analysis will be performed on all subjects treated in Cycle 1.

In detail, the following four steps will be performed:

1. One thousand completed datasets will be generated using the FCS statement with the regression method for arbitrary missing data patterns in SAS PROC MI. Variables considered will comprise maximum tremor amplitude at wrist level from previous visits¹², treatment, study site, gender⁹ [female/male], and age [years]. SAS code similar to the following will be used:

```
PROC MI DATA=dataset SEED=602011079 NIMPUTE=1000 OUT=mi_
  MINIMUM=. . . 0 0 0
  ROUND= . . . 1 1 1;
WHERE avisit="Week 6 (V4)" and param="Angular tremor
amplitude at wrist level dominant UL: Task with maximum
amplitude at study baseline";
CLASS SITEID SEX TRT01P;
FCS REG(BASE = TRT01P SITEID SEX AGE);
FCS REG(V3VAL = TRT01P SITEID SEX AGE BASE);
VAR TRT01P SITEID SEX BASE V3VAL AVAL;
RUN;
```

where SITEID = study site
SEX = gender
TRT01P = randomized treatment group
AVAL = maximum tremor amplitude at wrist level at Week 6 (V4)¹³
V3VAL = maximum tremor amplitude at wrist level at Week 4 (V3)¹³
BASE = study baseline value for maximum tremor amplitude at wrist level

2. The primary endpoint will be calculated from observed and imputed maximum tremor amplitude at wrist level at study baseline and at Week 6 (V4) in the completed datasets.
3. For each completed dataset, the primary endpoint will be analyzed by an ANCOVA model as defined in Section 4.1.1.1 whereby “ods output diffs=diff_mi LSMeans=lsm_mi” will be added to the SAS code.
4. The results from the 1000 imputed datasets will be combined for statistical inference using PROC MIANALYZE. SAS code similar to the following will be used:

¹² including study baseline value for imputation of missing values at Week 4 (V3) and study baseline and Week 4 (V3) values for imputation of missing values at Week 6 (V4).

¹³ calculated using measurements for the task with maximum tremor amplitude at study baseline

```
PROC MIANALYZE data=diff_mi;  
  MODELEFFECTS estimate;  
  STDERR stderr;  
  ODS OUTPUT ParameterEstimates=DIFF_MIAN;  
run;  
  
PROC MIANALYZE data=lsn_mi;  
  BY treatment;  
  MODELEFFECTS estimate;  
  STDERR stderr;  
  ODS OUTPUT ParameterEstimates=LSM_MIAN;  
run;
```

The following statistics will be displayed :

- n (number of values analyzed) and nimp (number of imputed values)
- LS Means of each treatment group (including SE and 95% CI)
- LS Mean treatment difference (including SE, 95% CI, and p-value).

All results from the above-described sensitivity analyses, including any CIs and p-values provided, will be interpreted descriptively only.

